Recently, authors have advocated for alternative methods of management of the predicted difficult airway, most commonly by using a video laryngoscope to perform the awake intubation. A video laryngoscope provides an indirect view of the larynx using a camera at the tip of a rigid laryngoscope. It takes less training to gain and maintain proficiency compared to flexible bronchoscopy.

Previous studies that have shown successful awake intubation with video laryngoscopy in the predicted difficult airway have not included patients with head and neck pathology, including malignancies or a history of head and neck surgery or radiation. Video

	Protocol Title:	Evaluation of Video Laryngoscopy in Patients with Head and Neck Pathology
	Principal Investigator Name/Contact Info:	[name] [contact]
	Primary Contact Name/Contact Info:	[name] [name]
	Date Revised:	3/13/2018
	Study Number:	GCO#17-0963/IF2253490

laryngoscopy may be more prone to failure in this patient population, and randomizing this population to video laryngoscopy would pose too great a risk.

If results of previous studies are erroneously generalized, anesthesiologists' skills in flexible bronchoscopy will decline. We therefore propose to perform video laryngoscopy in patients with head and neck pathology who require awake bronchoscopic intubation for surgery after placement of the tracheal tube and induction of anesthesia. This will allow us to approximate what the laryngeal view would have been with video laryngoscopy. If there is a significant incidence of difficult video laryngoscopy in this patient population, it will reinforce that anesthesiologists need to continue to learn and maintain skills in bronchoscopic intubation.

Objectives:

Research Question: In patients with predicted difficult airways due to head and neck pathology (malignancy or a history of surgery or radiation therapy) who undergo awake bronchoscopic intubation, what proportion would have been possible to intubate with video laryngoscopy?

Hypothesis: A significant proportion of patients with head and neck pathology will have poor laryngeal views with post-induction video laryngoscopy by experienced anesthesiologists.

Primary objective: Determine the incidence of difficult (Cormack-Lehane grade >2) video laryngoscopic view of the larynx after awake flexible bronchoscopic intubation in patients with head and neck pathology

Secondary objectives:

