Advantages cited for videolaryngoscopy include faster intubation time, less training required to gain and maintain skills, creation of space within the airway to suction secretions, view of the tracheal tube during intubation of the larynx (as opposed to blind “railroading” of the tube over the bronchoscope), lower cost, and easier maintenance of equipment. Disadvantages of videolaryngoscopy include possible increased risk of failure due to gag reflex unable to be attenuated with topical anesthesia, inability to use with very limited mouth opening, and inability to move around fixed lesions. While video laryngoscopy has a well-established role in management of the difficult airway, it does have recognized limitations and failures. There appears to be an increased risk of failure of video laryngoscopy in patients with airway masses, neck pathology, and neck radiation⁵ plausibly because a flexible scope would be required to move around immobile tissues. Neither direct nor indirect video laryngoscopy can accomplish this necessary flexibility. Randomizing this patient population, for whom awake flexible bronchoscopic intubation is the gold standard, to other techniques would be unsafe, as multiple laryngoscopies can increase the difficulty of airway management. As these patients have been excluded from previous randomized studies, the results of these studies cannot be generalized to the head and neck pathology patient population. This study aims to assess the utility of video laryngoscopy in this patient population by performing a video laryngoscopy after the endotracheal tube is safely secured by awake bronchoscopy to get an estimate of what the laryngeal view would have been had awake video laryngoscopy been used for the intubation. While laryngoscopy conditions are not identical after an endotracheal tube is already in place and the patient is anesthetized, it is the most appropriate study design to ensure safety in this patient population.

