Patients will be screened and consented on the day of surgery. The awake bronchoscopic intubation and asleep video laryngoscopy will be performed prior to the start of surgery. All patients will be seen in the hospital (or called at home postoperatively for ambulatory surgical patients) within 48 hours to assess for any delayed complications. As

	Protocol Title:	Evaluation of Video Laryngoscopy in Patients with Head and Neck Pathology
	Principal Investigator Name/Contact Info:	[name] [contact]
	Primary Contact Name/Contact Info:	[name] [contact]
	Date Revised:	3/13/2018
	Study Number:	GCO#17-0963/IF2253490

patients only need to be followed for a maximum of 48 hours after discharge to be assessed for all primary and secondary endpoints, we estimate the study will be complete within 2 weeks of final patient enrollment.

e) Study Endpoints

Primary objective: Determine the incidence of difficult (Cormack-Lehane grade >2) video laryngoscopic view of the larynx after awake flexible bronchoscopic intubation in patients with head and neck pathology.

Secondary objectives:

- a) grade the view (Cormack-Lehane) obtained by video laryngoscopy after awake flexible bronchoscopic intubation in patients with head and neck pathology
- b) grade the view (Cormack-Lehane) obtained by video laryngoscopy after awake flexible bronchoscopic intubation in patients with head and neck masses
- c) grade the view (Cormack-Lehane) obtained by video laryngoscopy after awake flexible bronchoscopic intubation in patients with a history of neck radiation

Subjects will be withdrawn from the study and video laryngoscopy will not be performed if the awake flexible bronchoscopy fails and the patient cannot be intubated, or if there is difficulty with the awake flexible bronchoscopy resulting in tissue trauma.

f) Procedures Involved in the Human Research

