Patients who are undergoing non-emergency surgery who have a history of head and neck pathology (masses, previous surgery, and/or radiation) who as determined by the anesthesiologist caring for the patient must undergo awake flexible bronchoscopic intubation will be invited to participate in the study after preoperative evaluation prior to entry into the operating room. Once in the operating room, intravenous access will be obtained and American Society of Anesthesiologists' standard monitors (pulse oximeter, electrocardiogram tracing, blood pressure cuff) will be applied. The patient will receive glycopyrrolate 0.2mg-0.4mg and sedation as per the usual practice of the anesthesiologist. Airway topicalization with lidocaine and awake flexible bronchoscopic intubation will be performed. After the tracheal tube is secured and general anesthesia is

	Protocol Title:	Evaluation of Video Laryngoscopy in Patients with Head and Neck Pathology
	Principal Investigator Name/Contact Info:	[name] [contact]
	Primary Contact Name/Contact Info:	[name] [name]
	Date Revised:	3/13/2018
	Study Number:	GCO#17-0963/IF2253490

induced, the attending anesthesiologist will perform video laryngoscopy with the C-MAC D video laryngoscope and with the GlideScope AVL video laryngoscope and grade the view of the larynx obtained with each laryngoscope. Care will be taken to minimize tissue trauma and hemodynamic perturbations caused by video laryngoscopy. All patients will receive 10mg of intravenous dexamethasone to reduce airway edema.

All participants will be monitored by the anesthesia team throughout the surgical procedure and until handoff of care to the Post-Anesthesia Care Unit (PACU) nurse as per usual practice. All subjects will be evaluated for the appearance of any delayed complications within 48 hours of the end of the procedure. Relevant data will be collected from the patient, anesthesiologist, EPIC, and Compurecord.

All medications administered and procedures performed are identical to those performed if not enrolled in the study, with the only exception being the video laryngoscopy.

Data to be collected:

Age
Gender
Body Mass Index (BMI)
Mallampati score
Head and neck pathology: 
 a) Location of mass, if present b) History of surgical procedure c) History of radiation
Visual Analog Score (VAS) of ease of bronchoscopic intubation by anesthesiologist

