[name] and [name] are board certified anesthesiologists with expertise in difficult airway management. All subjects will be monitored closely in the immediate perioperative period by the anesthesia team caring for the patient. Participants will also be seen postoperatively within 48 hours to assess for delayed complications, or called by telephone in the case of ambulatory procedures. Ambulatory participants will also receive instructions and a business card in order to have a point of contact to report a potential adverse event at any time during or after participation. They will also be specifically informed that they should receive emergency department care for any signs or symptoms of airway compromise. Any serious adverse event will be recorded by the research team in a non-anonymized fashion and reported directly to the Mount Sinai Institutional Review Board.

j) Withdrawal of Subjects

Subjects will be immediately withdrawn from the study if:

- Any difficulty resulting in airway injury occurs during the initial awake bronchoscopic intubation
- The awake bronchoscopic intubation is not able to be performed successfully

If withdrawn from the study, the anesthesiologist will not perform the planned laryngoscopy with the video laryngoscope.

5) Risks to Subjects

It is reasonably foreseeable that participants will have an increased risk of sore throat from the addition of video laryngoscopy.

Video laryngoscopy has the potential cause damage to oropharyngeal structures, including but not limited to: dentition, hard palate, soft palate, epiglottis, vocal cords, larynx, and soft tissue. These injuries are more likely to occur when struggling to obtain an adequate view of the larynx in order to intubate, which will not be the case for this study. Since the airway will be protected with an endotracheal tube during laryngoscopy, damage/ bleeding in the airway should not lead to issues with oxygenation or ventilation.

There is a risk of hemodynamic changes during laryngoscopy. The anesthesiologist will have the ability to treat tachycardia, bradycardia, hypertension, and hypotension with the appropriate pharmacologic agents.

	Protocol Title:	Evaluation of Video Laryngoscopy in Patients with Head and Neck Pathology
	Principal Investigator Name/Contact Info:	[name] [contact]
	Primary Contact Name/Contact Info:	[name] [name]
	Date Revised:	3/13/2018
	Study Number:	GCO#17-0963/IF2253490

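### Looks ended early to avoid trauma may inflate the incidence of difficult views by an unknown amount, and the data form cannot identify them

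*Combined protocol and SAP*

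**What the plan says.** Section 5 (Risks to Subjects) lists possible injuries from video laryngoscopy and says they are more likely "when struggling to obtain an adequate view of the larynx in order to intubate, which will not be the case for this study". Section 4f (Procedures) adds: "Care will be taken to minimize tissue trauma and hemodynamic perturbations caused by video laryngoscopy". In the same section the attending anesthesiologist uses two devices, the C-MAC D and the GlideScope AVL, and is to "grade the view of the larynx obtained with each laryngoscope". The data list in section 4f asks for one grade from 1 to 4 per device and for any complications. It has no item on how or why a look ended.

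The primary objective, in the Objectives and again in section 4e, is: "Determine the incidence of difficult (Cormack-Lehane grade >2) video laryngoscopic view of the larynx after awake flexible bronchoscopic intubation". The hypothesis is: "A significant proportion of patients with head and neck pathology will have poor laryngeal views with post-induction video laryngoscopy by experienced anesthesiologists". The research question reaches further and asks "what proportion would have been possible to intubate with video laryngoscopy". Section 1 (Background) likewise treats the grade as an estimate of the view that awake video laryngoscopy would have given. Its caveat, "While laryngoscopy conditions are not identical after an endotracheal tube is already in place and the patient is anesthetized", covers the tube and the anesthesia. It does not mention effort.

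**The concern.** The endpoint merges two different events. In one, the operator obtains the best view available and it is still grade 3 or 4. In the other, the operator stops at grade 3 or 4 because a better view does not seem worth the risk of trauma or circulatory change. Both are counted as difficult, and both feed a conclusion about what would have happened in an intubation attempt, where the operator would have had a reason to persist.

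Ending a look early can leave a grade unchanged or make it worse, but cannot improve it. Error from this source therefore has one sign. It raises the incidence, which is the result the hypothesis predicts and on which the argument for keeping bronchoscopy skills would rest. The operator also assigns the grade, no independent or blinded grading is described, and section 3 has the participating investigators briefed on the study objectives. If early stopping happens and is not recorded at the time, it cannot be reliably reconstructed later.

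**Working it through.** **Plan's own figure.** The only design figure is 100 subjects (section 4c). The documents give no expected incidence, precision target, alpha or power, so the sample size cannot be re-derived. They also give no frequency of early stopping. All rates below are assumptions.

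**Step 1: the texts side by side.**
- Section 5: no struggling for a view in order to intubate. Section 4f: keep trauma low.
- Section 4e: every grade above 2 is difficult, whatever the effort behind it.
- Objectives and section 1: the grade stands for the view in an intubation attempt.
- Section 4f data list: a grade only, so the two kinds of grade above 2 cannot be separated.

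If operators do pursue the best view in these predicted difficult airways, the reassurance in section 5 is less secure. If they do not, the grade is not what an intubation attempt would have shown. The documents do not say which applies.

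**Step 2: bounds for one device.** Let x be the number of looks out of 100 graded above 2, and e the number of those that ended early. The full-effort incidence lies between (x − e)/100 and x/100. With an assumed x = 30:
- e = 5: (30 − 5)/100 = 25%, so 25–30%
- e = 10: (30 − 10)/100 = 20%, so 20–30%
- e = 15: (30 − 15)/100 = 15%, so 15–30%

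Early-stopped looks already graded 1 or 2 do not matter, because they count as not difficult either way. As planned, e is not collected, so the range cannot be computed.

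**Step 3: effect on the estimate and its interval.** Let p be the full-effort rate and f the share of achievable grade 1–2 views recorded as above 2 because the look ended early. Then recorded rate = p + f(1 − p), and bias = f(1 − p). Coverage is the binomial probability, at n = 100 and the recorded rate, that the 95% Clopper-Pearson interval contains p.

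| p | f | recorded rate | bias (points) | coverage of p |
|---|---|---|---|---|
| 20% | 0 | 20% | 0 | 96.7% |
| 20% | 5% | 24% | 4 | 85.3% |
| 20% | 10% | 28% | 8 | 55.1% |
| 20% | 20% | 36% | 16 | 5.7% |
| 30% | 0 | 30% | 0 | 96.3% |
| 30% | 5% | 33.5% | 3.5 | 89.5% |
| 30% | 10% | 37% | 7 | 70.0% |
| 30% | 20% | 44% | 14 | 18.3% |

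Over p = 10–40% and f = 5–20%, the bias runs from 0.05 × 0.60 = 3 points to 0.20 × 0.90 = 18 points. For scale, the 95% interval at n = 100 is 12.7–29.2% for 20/100 and 21.2–40.0% for 30/100.

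**Step 4: a counter-effect.** Patients whose bronchoscopy fails or causes injury get no grade (section 4j: "If withdrawn from the study, the anesthesiologist will not perform the planned laryngoscopy with the video laryngoscope"). Suppose, as an extreme, that 5% are withdrawn and all would have been difficult. A 20% rate becomes (0.20 − 0.05)/0.95 = 15.8%, down 4.2 points. A 30% rate becomes (0.30 − 0.05)/0.95 = 26.3%, down 3.7 points. These falls are about as large as the rises at f = 5% (4 and 3.5 points).

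**The case against.** The strongest reply is that no effort limit exists. Section 5 is a risk disclosure and can be read to mean only that nobody needs to struggle because the airway is already secured. Section 4f expresses general care. Neither sets a rule on time, attempts or stopping. This stands: a reader might infer that the protocol caps operator effort, and the text does not say so. The measurement gap remains even on the milder reading, because nothing defines or records whether the graded view was the best obtainable one.

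A reader might also infer that the operator has no clinical use for a better view. The documents do not support that. Section 16 puts the view in the anesthesia record and offers discussion of notable results, and section 5 names the video laryngoscope as one option if reintubation is needed.

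The size is unknown, and with the experienced operators described in section 3 it may be near zero. This stands. Other features may push the incidence down: the withdrawals in step 4, and general anesthesia, since section 1 names the gag reflex as a cause of failure in awake use. This also stands, but withdrawals can be counted and reported, whereas early-stopped looks, as planned, cannot.

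Finally, section 1 already concedes that conditions differ from a real intubation, and the endpoint is worded as a view. The caveat does not extend to effort, however, and the research question does extrapolate to intubation.

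**Conclusion.** The point holds in a limited form. Because effort is neither standardised nor recorded, looks ended early to avoid trauma or hemodynamic change may inflate the incidence of grade above 2. That source of error can act only upward, toward the hypothesis.

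The documents do not show that the primary result is inflated, or that the net bias is upward. Both are tempting inferences, but the frequency of early stopping is not given and opposing influences exist. The 30 per 100 with 5 to 15 early stops, and the 3 to 18 points under the assumed p and f, illustrate sensitivity and are not estimates. They also apply to one device at a time, because section 4e does not say which device, or what combination, defines a difficult view for a patient.

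The change is still worth making before data are collected, since it decides whether the incidence can be interpreted at all with respect to effort.

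**What to change.** Leave the safety provisions as they are.

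1. **Data form (section 4f).** For each device, next to the grade, have the operator mark one of two options: *best obtainable view reached*, or *look ended early to avoid trauma or hemodynamic change*. The protocol initiation meeting in section 3 can be used to explain the options so that operators apply them alike.
2. **Reporting.** Give the incidence of grade above 2 per device as planned. Also give a range in which early-stopped looks graded above 2 are counted first as none difficult and then as all difficult.
3. **Section 4e.** State that the grade is a view obtained without the persistence of an intubation attempt, so the incidence is an upper estimate as far as effort is concerned.
4. **Consistency.** Reconcile sections 4f and 5 with the endpoint in section 4e. How far effort may go is a clinical safety matter, and no limit is proposed here.

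The cost is one extra form item per device and one further line of results. The item is self-reported by an operator who is not blinded, so it reduces the ambiguity without removing it. If early stopping proves common, the headline becomes a range. If it proves rare, the planned figure is strengthened.
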